8.3.2. Secondary Variables

8.3.2.1. Primary and Secondary Safety Variable Characteristics

Any primary or secondary safety variable event available in the data source will be further detailed regarding symptoms, diagnostic processes, and treatments. This includes but will not be limited to imaging, antithrombotic treatment, hospitalisation status and current additional treatments for haemophilia when available (see section

8.3.1. on the details provided in the respective data sources adverse event reporting system).

8.3.2.2. Exposure Definition

Exposure will be based on dates of prescriptions and dispenses, and details on the numbers of prescriptions and doses, as reported in the data source. The start of exposure (index date) is defined as the first prescription or injection of emicizumab, as noted in the data source. An overview of the variables available to define exposure during follow-up can be seen in Table 4. All registers cover the haemophilia related treatments: emicizumab, aPCC, Eptacog alfa (activated), and Factor VIII transfusions.

If the registry does not include information on exact stop dates of treatment exposure, as in the case of HemoNED, treatment will be considered ongoing for as long as new prescriptions, injections or dispenses are noted in the data source and are consistent with continuous treatment. To accommodate non-perfect adherence or other situations where the series of prescriptions are part of a continuous exposure period, an additional 90 days will be added to exposure period, at the last noted injection or at the end of prescribed supply, corresponding to 3 times the half-life of emicizumab when the patient will be considered no longer affected by the drug (Hallare and Gerriets, 2023). If the patient has not filled another prescription or received an injection at the end of the added 90 days, the exposure period will end. The definition of exposure might differ between data source and will be further defined in the SAP. Reason for treatment discontinuation will also be collected where available. Exposure of other treatments of interest, that were given prior to the index date, will be defined using a similar methodology that will be detailed in the SAP.

Hemlibra—F. Hoffmann-La Roche Ltd Protocol BO44691, Version 2.0

Register	Country	Start / stop dates	Dosage	Frequency	Reason for treatment*
UKNHD	UK	Captured	Captured	Captured	Captured
FranceCoag	France	Good	Good	Derived	Good
HemoNED	Netherlands	Moderate (start only)	Captured	Captured	Captured
ATHNdataset	US	Good	Good	Good	Good
WBDR	Multi- country	Good	Good	Good	Good
CBDR	Canada	Good	Good	Good	Good

Table 4. Treatment information in each data source.

*Prophylaxis, on demand or other.

UKNHD, UK National Haemophilia Database; **UK**, United Kingdom; **ATHNdataset**, American Thrombosis and Hemostasis Network; **US**; United States; **WBDR**, World Bleeding Disorders Registry; **CBDR**, Canadian Bleeding Disorders Registry.

Information from feasibility questionnaire or data dictionary: Good = >70% patients included in the disease registries have the required variable, Moderate = 40 - 70% patients with variable, Low <40% patients with variable, Captured = Not disclosed, Derived = Derived from other variables in the dataset, Not collected = No patients with variable.

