8.2.3. Index date

The index date will be the date of emicizumab treatment initiation for each patient during the cohort entry period.

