8.2.6. Study Populations

HA patients that are naïve users of emicizumab will be selected based on the eligibility criteria presented below.

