Information from feasibility questionnaire or data dictionary: Good = >70% patients included in the disease registries have the required variable, Moderate = 40 - 70% patients with variable, Low <40% patients with variable, Captured = Not disclosed, Not collected = No patients with variable.

The above-mentioned inclusion criteria will ensure that the patient is eligible for the extended indication of emicizumab.

In addition, the patient will have to fulfil the following criteria:

- Initiation of emicizumab treatment during the cohort entry period.
- Information on previous HA outcomes and HA treatments approximately 12 months prior to the index date. In case HA diagnosis occurred within 12 months of the index date, the required lookback period will be shortened to time from HA diagnosis to index date. Anamnestic information capturing historic events but entered in the

Hemlibra—F. Hoffmann-La Roche Ltd

Protocol BO44691, Version 2.0

registry database less than 12 months before the index date will be considered as long as they were recorded prior to the index date.

- Information on risk factors of TE events (e.g., medical comorbidities, treatments and demographic characteristics) approximately 12 months prior to the index date. If the patient is below 1 year of age, the lookback period will be shortened to birth until index date. Anamnestic information capturing historic events but entered in the registry database less than 12 months before the index date will be considered as long as they were recorded prior to the index date.
- Signed the informed consent form where required by local regulations.

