8.2.6.2. Exclusion Criteria

Patients will be excluded from the study if they meet any of the following criteria:

- Noted development of FVIII inhibitors in the data source any time before index date or fulfilling any of the following criteria of a previously developed algorithm (Batt et al., 2022):
 - Treatment with bypassing agents, such as aPCC or recombinant activated FVII (rFVIIa), at any time prior to the index date.
 - Treatment with rituximab at any time prior to the index date, this criterion would not apply if it was noted in the data source that it was used for another indication, e.g., treatment of lymphoma.
 - Noted use of assay to measure FVIII inhibitors (Duncan et al., 2013) and high dose of FVIII use at any time prior to the index date that is in line with immune tolerance induction. The exact definition of dosage in line with immune tolerance induction will be further defined in the statistical analysis plan (SAP) and may be data source specific.
- Treated with emicizumab at any time prior to the index date.

These criteria will ensure that the patient is eligible for the extended indication of emicizumab.

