8.9.2. Information Bias

Information bias is the bias arising from the systematic measurement error or misclassification of patients. As this is a registry-based study the validity of the findings of the study will solely rely on the validity, quality and completeness of the information recorded in the registries. There is potential for heterogeneity in the type of data collected from the registries regarding emicizumab treatment exposure, e.g., the exact dates of dispenses and SC injections, that could potentially result in exposure misclassification that are registry specific. Depending on the registry, specific limitations for exposure classification could be developed to avoid misclassification. There is also potential for heterogeneity in the study population because of different lookback periods when patients enrol in different registries. In certain cases, the lookback period might not be fully 12 months and the inclusion criteria regarding previous HA outcomes and HA treatments approximately 12 months prior to the index date (see section 8.2.6.1.) may not be fully confirmed if emicizumab treatment initiation (index date) coincides with patient enrolment into the registry.

In the primary incidence analysis, we do not exclude patients with a history of TE events before the index date. Thus, there exists a possibility that individuals with prior TE **Hemlibra—F. Hoffmann-La Roche Ltd**

Protocol BO44691, Version 2.0 events are included in the crude IR of TE. In the planned analysis of secondary objective 4 the IR would be tabulated based on the history of TE events during the lookback period. This would ensure that the incidence would be calculated for patients treated with emicizumab without any prior TE events during the lookback period and in addition contribute valuable evidence on the event rate among patients treated with emicizumab who have a history of TE events.

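### The index date rests on the first emicizumab record in the registry, so where the true start date is not held the naive-user exclusion cannot detect earlier treatment

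*Protocol*

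**What the plan says.** The protocol gives the index date in two ways. Section 8.2.3 reads: "The index date will be the date of emicizumab treatment initiation for each patient during the cohort entry period"; section 8.2.4 likewise starts follow-up at first initiation. Section 8.3.2.2 makes this operational: "The start of exposure (index date) is defined as the first prescription or injection of emicizumab, as noted in the data source".

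The intended cohort is stated in 8.2.6: "HA patients that are naïve users of emicizumab will be selected". Section 8.2.6.2 excludes patients meeting this criterion: "Treated with emicizumab at any time prior to the index date".

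Section 8.2.6.1 adds a lookback requirement: "Information on previous HA outcomes and HA treatments approximately 12 months prior to the index date". History entered late in the registry "will be considered as long as they were recorded prior to the index date". No minimum registry enrolment before the index date is stated.

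Section 8.9.2 accepts that the lookback criteria "may not be fully confirmed if emicizumab treatment initiation (index date) coincides with patient enrolment into the registry". It treats this as heterogeneity of the population and does not say whether such patients stay in.

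Table 4 rates start and stop dates as good (more than 70% of patients) in FranceCoag, ATHNdataset, WBDR and CBDR. HemoNED is moderate (40-70%) with start dates only, and UKNHD holds the field with completeness not disclosed. Section 8.3.2.2 also says that the exposure definition may differ by data source and will be further defined in the SAP, which is not at hand.

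**The concern.** In a new-user cohort, follow-up should begin at the first dose. If the index date is the first record in the registry, then by construction no recorded prescription or injection precedes it. The exclusion for prior emicizumab then works only where earlier use is recorded in some other way, for example as history or as a start date.

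A patient who joined a registry while already on emicizumab, with no true start date entered, could pass as naive. Three things would follow:

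- Time zero of the person-time and of the Kaplan-Meier curves would be too late.
- A thromboembolic (TE), TMA or hypersensitivity event suffered on emicizumab before enrolment would fall before the index date. A TE event would at most count as the risk factor of a previous TE event (8.3.2.4), not as an outcome.
- The later person-time, conditional on having tolerated the early doses, would still enter the denominator (8.7.2).

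The study exists to characterise TE risk in this population, so a distortion that may run towards a lower rate deserves a safeguard.

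**Working it through.** **1. The passages side by side**

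| Section | Rule | Patient indexed on enrolment day |
|---|---|---|
| 8.2.3, 8.2.4 | Index = treatment initiation | Correct only if the true start is that day |
| 8.3.2.2 | Index = first prescription or injection noted | Index = enrolment day if nothing earlier is noted |
| 8.2.6.2 | No emicizumab before index | Passes if earlier use is unrecorded |
| 8.2.6.1 | Late-entered history must be recorded before index | Fails on a strict reading |
| 8.9.2 | Lookback may be unconfirmed in this case | Contemplated; handling not stated |

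Sections 8.2.6.1 and 8.9.2 point in different directions for the same patient. Neither separates a true starter enrolled that day from a patient already on treatment. None of the four sensitivity analyses in Table 10 varies this: they change censoring at discontinuation, event counting, the five-year cap and the bleeding-phenotype definition.

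**2. Where a check can be applied**

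Table 7 gives no patient-level access for WBDR (2987 moderate patients) and CBDR (299). Together that is 2987 + 299 = 3286 of 5307, or 62%. There the data holder applies the common data model to specifications it receives (8.6), so a rule comparing start date with enrolment date has to be in those specifications. It cannot be applied to aggregates afterwards.

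**3. Direction and size of bias (illustration only)**

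The documents give neither the share p of patients already on treatment nor how the hazard changes with time on drug. Assume a hazard k times the later hazard in the first 6 months, 4 years of follow-up for all, and p between 5% and 50%.

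- Mean relative rate in true new users: R = (0.5k + 3.5)/4. This is 1.000 for k = 1, 1.125 for k = 2 and 1.375 for k = 4.
- Patients already past the first 6 months have relative rate 1.
- Relative fall in the pooled rate: p(1 - 1/R).

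| p | k = 1 | k = 2 | k = 4 |
|---|---|---|---|
| 5% | 0% | 0.6% | 1.4% |
| 20% | 0% | 2.2% | 5.5% |
| 50% | 0% | 5.6% | 13.6% |

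With a constant hazard there is no bias in the crude rate. With a hazard that rises over time the sign reverses. For an outcome confined to the first doses, the fall equals p.

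**4. Effect of the fix on the stated precision**

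The protocol's figure (8.5.2, Table 9) reproduces. 200 patients x 4 years = 800 person-years (PY), and 0.15 per 100 PY gives 1.2 expected events. The exact 95% upper limit for 2 events is 7.22/800 = 0.90 per 100 PY, and for 3 events 8.77/800 = 1.10. So at most 2 events are allowed, and P(X <= 2 | 1.2) = 0.879, against the stated 88%.

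Two events remain allowed only down to about 720 PY (Clopper-Pearson limit), which is 180 patients. Starting from the projected 202, with assumed losses:

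| Loss | Patients | PY | Events allowed | Probability |
|---|---|---|---|---|
| 0% | 202 | 808 | 2 | 88% |
| 5% | 192 | 767 | 2 | 89% |
| 10% | 182 | 727 | 2 | 90% |
| 11% | 180 | 719 | 1 | 71% |
| 20% | 162 | 646 | 1 | 75% |
| 30% | 141 | 565 | 1 | 79% |

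The jump between 10% and 11% comes from the discreteness of the event count. The slow rises on either side of it reflect fewer expected events, not better precision.

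**The case against.** A reader might infer that every patient who enrols while on emicizumab enters as a new user, that the exclusion can never remove such a patient, and that the rates are therefore substantially understated. The documents do not support that.

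- Sections 8.2.3 and 8.2.4 tie the index date to treatment initiation, and the phrase in 8.3.2.2 can be read as the date of the first dose, taken from the registry. A start-date field may predate enrolment, and four of six registries rate it good. Where it is filled in, the index date is correct, and a recorded start before the cohort entry period disqualifies.
- The exclusion is not worded as limited to registry-noted use, and history may be used. Even so, a secondary-data study can apply it only through what is recorded.
- Read strictly, 8.2.6.1 removes a patient with no registry history before the index date. Section 8.9.2 is limitations text about patients initiating at enrolment and sets no eligibility rule.
- WBDR holds 2987 of 5307 moderate patients (56%), but that is its share of all moderate patients. It says nothing about how many emicizumab users were already treated at enrolment.
- A downward bias needs a hazard that falls with time on drug, which the documents do not show. Even the largest TE figure illustrated above would move 0.15 to about 0.13 per 100 PY, inside the cited interval of 0.03 to 0.44.
- Source-specific exposure rules are left to the SAP.

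These arguments limit the size of the problem. They do not remove the mismatch in the index-date anchor or the conflict between 8.2.6.1 and 8.9.2. Both are fixed in the protocol's own text and concern eligibility and time zero, not programming detail.

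**Conclusion.** The point holds as a gap in protecting the naive-user design. The index date is anchored to the registry record in one section and to treatment initiation in others. Where the true start date is not held, the prior-emicizumab exclusion cannot detect earlier unrecorded treatment, and the lookback backstop is contradicted by the limitations section. Patients already on treatment could therefore enter with a wrong time zero and with on-treatment events classed as history.

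The rates fall only if risk is concentrated early, and by an amount the documents do not allow to be estimated. The percentages under step 3 rest wholly on assumed shares and hazard ratios. No figure stated in the protocol is wrong on this point: Table 9's 88% and the projection of 202 both reproduce (3000 x 0.9 x 0.3 x 0.25 = 202.5).

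**What to change.** Reconcile sections 8.2.3, 8.2.6.1, 8.3.2.2 and 8.9.2:

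1. Define the index date as the documented first-ever emicizumab start.
2. For the primary rate, require either a registry or treatment record before the index date without emicizumab, or an explicit first-ever start date equal to the enrolment day. In the second case, same-day baseline data count as pre-index information.
3. Report patients enrolled while already on emicizumab, or with an unknown start date, separately from the primary rate. At minimum, add to Table 10 a sensitivity analysis restricted to patients enrolled before their first emicizumab record.
4. Put the rule in the data specification sent to registries that supply only aggregates.

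The cost is wording in the protocol and data specification, plus some patients leaving the primary rate, chiefly where start dates are incomplete. If more than about 10% of the projected 202 are lost, the 88% falls to about 71% and should be restated. That projection is the lowest of the four scenarios in Table 8 (202 to 540), so there may be room. The sensitivity analysis alone leaves the primary sample intact.

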8.3.2.3. Patient Characteristics

The following patient characteristics will be collected from the data sources:

- Age
- Sex
- Ethnicity
- Weight
- Height
- Country of residence
- Date of diagnosis of congenital HA
- Any major complications (e.g., bleeding events, hemarthrosis, infections from injections)
- Prior treatments for haemophilia
- Concomitant medications
- Other medical history and concurrent conditions

The coverage of the different demographic and clinical characteristics in the considered registries shown are shown in Table 5 and Table 6.

Hemlibra—F. Hoffmann-La Roche Ltd Protocol BO44691, Version 2.0

Table 5. Der	nographic	charact	eristics.
--------------	-----------	---------	-----------

Data source name	Country	Age	Sex	Ethnicity	Weight and height
UKNHD	UK	Captured	Captured	Captured	Captured
FranceCoag	France	Good	Good	Good	Good
HemoNED	Netherlands	Captured	Captured	Captured	Captured
ATHNdataset	US	Good	Good	Good	Good
WBDR	Multi- country	Good	Captured	Not collected	Good
CBDR	Canada	Good	Good	Low	Good

UKNHD, UK National Haemophilia Database; **UK**, United Kingdom; **ATHNdataset**, American Thrombosis and Hemostasis Network; **US**; United States; **WBDR**, World Bleeding Disorders Registry; **CBDR**, Canadian Bleeding Disorders Registry.

Information from feasibility questionnaire or data dictionary: Good = >70% patients included in the disease registries have the required variable, Moderate = 40% - 70% patients with variable, Low <40% patients with variable, Captured = Not disclosed, Not collected = No patients with variable.

Hemlibra—F. Hoffmann-La Roche Ltd Protocol BO44691, Version 2.0

Data source	HA diagnosis	HA disease severity	HA treatments*	HA medical history	FVIII inhibitors	Laboratory measures	Current comorbidities	Concomitant medications
UKNHD	Good	Good	Good	Captured	Captured	Moderate	Captured	Captured
FranceCoag	Good	Good	Good	Moderate	Captured	Not collected	Good	Low
HemoNED	Captured	Captured	Captured	Captured	Captured	Moderate	Pending	Pending
ATHNdataset	Good	Good	Good	Good	Captured	Moderate	Good	Good
WBDR	Good	Good	Good	Good	Captured	Moderate	Good	Good
CBDR	Good	Good	Good	Good	Captured	Low	Low	Not collected

Table 6. Clinical characteristics.

*Treatment with emicizumab, Anti-inhibitor coagulant complex use, Eptacog alfa (activated), FVIII.

HA, Haemophilia A; FVIII, Coagulation Factor VIII; UKNHD, UK National Haemophilia Database; UK, United Kingdom; ATHNdataset, American Thrombosis and Hemostasis Network; WBDR, World Bleeding Disorders Registry; CBDR, Canadian Bleeding Disorders Registry.

Information from feasibility questionnaire or data dictionary: Good = >70% patients included in the disease registries have the required variable,

Moderate = 40 – 70% patients with variable, Low<40% patients with variable, Captured = Not disclosed, Not collected = No patients with variable, Pending = Information requested from data source, awaiting reply.

8.3.2.4. Risk Factor Variables for TE Events

The following candidate variables will be used to characterise the patients TE risk profile and are assessed within one year prior to the index date. The candidate risk factors were chosen based reference literature regarding their relationship with TE events (den Heijer et al., 1996; Goldhaber, 2010; Heit, 2015; Keramidas et al., 2021; Lowe, 2008; Pastori et al., 2023; Raj et al., 2022). As the feasibility assessment did not provide detailed information on the availability of all TE risk factors, a full evaluation of the availability of the risk factors in each data source will be provided in the SAP. Risk factors considered to be included:

Patient characteristics:

- Advanced age (age > 50 years)
- Smoking
- Body Mass Index (BMI) (BMI ≥ 30 kg/m² i.e., obesity)
- Sex

Patient medical history:

- Previous TE event
- Venous insufficiency
- Myocardial infarction
- Ischaemic heart disease
- Coronary artery disease
- Cerebrovascular disease
- Peripheral vascular disease
- Heart failure
- Hypertension
- Atherosclerosis
- Diabetes
- Medical device use
- Moderate or severe liver disease
- Recent hospitalisation/surgery
- Previous or ongoing cancer
- Chronic Inflammatory Lung Diseases (including Chronic obstructive pulmonary disease [COPD], asthma, tuberculosis)
- Obstructive sleep apnea

Hemlibra—F. Hoffmann-La Roche Ltd Protocol BO44691, Version 2.0

- Lower limb paralysis
- Hyperhomocysteinemia
- Chronic kidney disease Stage 3 and above
- Recent trauma/ fractures
- Hormone replacement therapy including oral contraceptives
- Pregnancy/puerperium
- Infectious diseases (including sepsis, pneumonia, Covid-19 infection and Human Immunodeficiency Virus infection)
- Inflammatory disorders (including systemic lupus erythematosus [SLE], inflammatory bowel disease and rheumatoid arthritis)

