For each event reported, data are collected on the patient's age, diagnosis and severity; as well as details about the product and batch numbers involved; and finally details about the event outcome and presence of other risk factors (Makris et al., 2011). Event-specific data are submitted anonymously using the Soundex coding system to avoid

Hemlibra—F. Hoffmann-La Roche Ltd

Protocol BO44691, Version 2.0

duplicate reporting. EUHASS data are not collected according to the medical dictionary for regulatory activities (MedDRA) classifications; however, AEs have been previously aligned to MedDRA preferred terms.

For the UKNHD data source, event reporting has been harmonised with the EUHASS program, and any reported event from participating centres are anonymised and automatically forwarded to EUHASS by the National Haemophilia Database (NHD). Yet, whenever a new inhibitor is reported, the UK Haemophilia Centre Doctors' Organisation (UKHCDO) requests more detailed information, which is not passed onto EUHASS. The additional data requested by the UKHCDO when a new inhibitor is reported include (World Federation of Hemophilia, 2009):

- Coagulation disorder, severity, and genotype if known
- Any relatives with inhibitors
- First inhibitor detection date and the reason for the test
- Inhibitor value at first detection and maximum value
- Any change in the value of factor VIII- or factor IX-coagulant (FVIII:C or FIX:C)
- Any change in bleeding pattern
- Treatment protocol before inhibitor development
- Time in chronological and exposure days from first dose to inhibitor development

The Canadian Hemophilia Surveillance System (CHESS) uses the same methodology as the EUHASS program (Dolan et al., 2014).

For the WBDR data source, an AE module is available at both baseline (when the patient enrolled in the registry) and follow-up visits. When an AE is reported, the participant centre must complete the following fields:

- Start date of onset (i.e., the date the patient first experiences the AE)
- Events (Infection, allergic reaction including anaphylaxis, TE event, TMA, lack of efficacy, injection site reaction or other event)
- Date of resolution (i.e., the date by when the patient stops experiencing the AE)
- Interventions

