8.7.2. Planned Analyses

For the analysis of the primary objective and secondary objectives 1, 2, and 3 the overall crude and crude stratified IRs will be calculated. The person-time of each patient will be based on the follow-up and censoring criteria presented in section 8.2.4. and 8.2.5.

For the calculation of crude IRs, the denominator will be the pooled person-time of all the patients within the cohort. The patient time-at-risk will be calculated from index date until the date of an incident event or censoring, whichever occurs first. All first events occurring during follow-up period will be counted in the total number of events. Crude IRs will be presented per 100 PY with 95% CI.

For the primary objective, the numerator will be the number of first TE events of all patients within the cohort. For secondary objectives 1, 2, 3 the numerator will be the number of first occurrences of any SAE; TMA events or serious systemic hypersensitivity reactions, including anaphylaxis; respectively.

For the analysis of secondary objective 4, calculation of crude stratified IRs of 1st TE events will be done. The events will be counted for each category/stratum of relevant pre-defined risk factors (see section 8.3.2.4. for a listing of considered risk factors). More details on the risk factor based tabulations will be presented in SAP.

For analysis of secondary objective 5, characteristics of TE events, SAEs, TMA, and serious systemic hypersensitivity reactions, including anaphylaxis (e.g., diagnosis and symptoms), will be tabulated. In addition, time to 1st TE event; time to 1st TMA event; time to 1st serious systemic hypersensitivity reactions, including anaphylaxis; and time to any 1st SAE event will be described by Kaplan-Meier curves.

For analysis of secondary objective 6, calculation of crude IR and crude incidence proportion of TE, TMA events, SAEs and serious systemic hypersensitivity reactions, **Hemlibra—F. Hoffmann-La Roche Ltd** Protocol BO44691, Version 2.0

including anaphylaxis, will be calculated and tabulated for FVIII prophylaxis use (yes/no) prior to emicizumab treatment.

Patient demographic and clinical characteristics will also be tabulated in relation to the AEs (TE events, SAEs, TMA events and serious systemic hypersensitivity reactions, including anaphylaxis) and in total.

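### Short-lived thrombosis triggers are recorded only in the year before index, so strata built on them say little about TE risk over 4 to 5 years of follow-up

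*Protocol*

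**What the plan says.** Section 8.3.2.4 lists 29 candidate risk factors under one timing rule: they "will be used to characterise the patients TE risk profile and are assessed within one year prior to the index date". Most are lasting, such as diabetes, atherosclerosis or chronic kidney disease. Some are not: "Recent hospitalisation/surgery", "Recent trauma/ fractures" and "Pregnancy/puerperium". The infection item is mixed: "Infectious diseases (including sepsis, pneumonia, Covid-19 infection and Human Immunodeficiency Virus infection".

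Section 8.7.2 uses the list for secondary objective 4, where crude rates of first TE events are calculated by stratum: "The events will be counted for each category/stratum of relevant pre-defined risk factors". Section 8.2.4 caps follow-up at 5 years, and sensitivity analysis 3 in Table 10 removes the cap. Section 8.7.3 likewise fixes subgroup variables at index.

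No section updates a risk factor after index. None of the sensitivity analyses in Table 10 varies the assessment time, and section 8.9 does not list it as a limitation. The SAP is to supply the availability of each factor (8.3.2.4) and details of the tabulations (8.7.2). The protocol itself sets the assessment time.

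For each TE event, Table 2 lists number, diagnosis, start date, outcome, relatedness and treatment. Section 8.3.2.1 adds symptoms, diagnostic work-up, hospitalisation status and current additional haemophilia treatment, as an open-ended list. Neither names surgery, trauma or infection around the event. Section 8.3.1 says that EUHASS event reports hold "details about the event outcome and presence of other risk factors", and that CHESS follows the same method.

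**The concern.** A factor such as diabetes recorded before index still describes the patient four years later. An operation ten months before index does not. Under the stated rule, that patient contributes up to 5 years of person-time, and any TE event, to the 'recent surgery' stratum. A patient with no operation in the lookback who is operated on in year 3 and has a thrombosis two weeks later is counted under 'no recent surgery'. For such factors the stratum rate mostly describes time in which the trigger is no longer acting.

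The study exists to characterise TE events not associated with aPCC (section 6.2), and about one is expected. With so few, the circumstances of each event are the most informative evidence. Where a registry does not record relatedness, the fallback named in section 8.3.1 is time to first event, which does not show whether a trigger was present.

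**Working it through.** **Inputs from the protocol.** Lookback 1 year (8.3.2.4); maximum follow-up 5 years (8.2.4); 200 patients with an average of 4 years, expected rate 0.15 per 100 PY, threshold 1 per 100 PY, stated probability 88% (8.5.2); registry counts (Table 7).

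**1. The plan's own figure.**
- Person-time: 200 × 4 = 800 PY. Expected first TE events: 800 × 0.0015 = 1.2.
- The two-sided 95% Clopper-Pearson upper limit on 800 PY is 0.90 per 100 PY for 2 events and 1.09 for 3, so at most 2 events are allowed.
- P(X ≤ 2) with mean 1.2 = e^(−1.2) × (1 + 1.2 + 0.72) = 0.301 × 2.92 = 0.88. The stated 88% is reproduced.
- P(no event) = e^(−1.2) = 0.30.

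This calculation does not involve the risk-factor strata, so it is the same whatever assessment time is used.

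**2. Follow-up in the 'yes' stratum that lies beyond the trigger window.** The latest possible lookback trigger is at index. With window w and completed follow-up T, and no new trigger, the share beyond the window is at least (T − w)/T.
- w = 12 months: (4 − 1)/4 = 75%; (5 − 1)/5 = 80%.
- Shorter windows are assumptions, since the protocol does not define 'recent'. For a 60-month follow-up, the share inside the window is at most 1/60 = 2%, 3/60 = 5% and 6/60 = 10% for windows of 1, 3 and 6 months.

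These are best cases, with the trigger on the day of index. If triggers spread evenly over the lookback (assumption):
- 12-month window: mean remaining time is 0.5 year, so 1 − 0.5/4 = 87.5% of a 4-year follow-up lies beyond it.
- 3-month window: a quarter of the triggers are still active at index, with 0.125 year left on average, so 1 − (0.25 × 0.125)/4 = 99% lies beyond it.

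**3. Events that could fall in the 'no' stratum (illustration; p, window and rate ratio are not in the protocol).** Let p be the annual trigger probability, the same before and after index and independent between years, with a 3-month window and rate ratio RR inside it.
- Share of person-time inside a window: f = 0.25p.
- Rate outside a window: r0 = 0.0015 / (1 − f + f × RR).
- Events inside a window in patients with no baseline trigger: 800 × f × r0 × RR × (1 − p).
- Example, p = 0.10 and RR = 5: f = 0.025; r0 = 0.0015/1.10 = 0.001364; 800 × 0.025 × 0.001364 × 5 = 0.136; × 0.9 = 0.12.
- Over p = 0.05 to 0.20 and RR = 2 to 10, the result is 0.03 to 0.33 of the 1.2 events.

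The baseline 'yes' stratum would hold 800p = 40 to 160 PY and 0.06 to 0.24 expected events. With no event in it, the exact Poisson upper limit is 3.69/40 = 9.2 down to 3.69/160 = 2.3 per 100 PY.

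**4. Where event-level information could come from (Tables 3 and 7, section 8.3.1).**
- EUHASS, its local adaptation, or CHESS: UKNHD, FranceCoag, HemoNED and CBDR, with 836 + 940 + 230 + 299 = 2305 of 5307 moderate patients (43%).
- WBDR: 2987 of 5307 (56%). The adverse-event fields listed for it are onset date, event type, resolution date and interventions, with no risk-factor item.
- WBDR and CBDR give no patient-level access. Their providers aggregate to a pre-specified data model (8.6), so a field has to be specified to be delivered.

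**The case against.** The strongest reply is that a stratum meaning 'factor recorded in the year before starting emicizumab' is an ordinary baseline stratum. Its person-time is correctly assigned, and objective 4 asks for a risk profile of the patient population. That stands. A reader might take the 90% to 98% of follow-up lying outside a 1 to 6 month window as misclassified person-time. The protocol does not support this, because it never defines the stratum as current presence within a risk window.

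A reader might also infer that every trigger after index is counted under 'no'. It is not: a patient with a trigger before index and another later is in the 'yes' stratum. Nor does a place in a baseline 'no' stratum label an event unprovoked or attribute it to the drug. The study makes no formal comparison (8.7.1), so no contrast between strata is decided by one event.

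Further, the list is one of candidates, section 8.7.2 speaks of relevant factors, and the SAP may leave transient ones out of the rate tables. Section 8.3.2.1 is open-ended and refers to the adverse-event systems, so event-time risk factors could be reported without a protocol change. Both are fair. They leave room for a good analysis but do not commit to one, and the assessment time is not left open.

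Lastly, with 1.2 expected events and 29 factors, the stratum rates will be very imprecise under any window. This also stands. It favours an event-level remedy over time-updated strata.

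**Conclusion.** The point holds as a modest improvement to secondary objectives 4 and 5. For recent hospitalisation or surgery, recent trauma or fracture, acute infection, and pregnancy or puerperium, the baseline stratum says little about TE risk during follow-up. At least 75% to 80% of a completed 4 to 5 year follow-up in the 'yes' stratum is beyond even a 12-month window, and a TE event after a first trigger during follow-up can fall under 'no'. The 75% to 80% assumes completed follow-up and no new trigger; it does not apply to patients censored early. The 0.03 to 0.33 misplaced events rest wholly on assumed trigger frequencies, a 3-month window and assumed rate ratios.

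Lasting factors are not affected in this way, including HIV within the infection item and long-term device use. The crude TE rate, the target of about 200 patients and the 88% do not change, and the study's main conclusion does not depend on this point.

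**What to change.** 1. In 8.3.2.4, separate lasting from transient factors. Keep the lasting ones, including HIV and long-term device use, as baseline strata for objective 4.
2. Use the transient triggers to describe the cohort at baseline only, and state in 8.7.2 that they do not define strata for TE rates.
3. In Table 2 and 8.3.2.1, name for each TE event the risk factors present at or shortly before it, with a stated window, taken from the EUHASS- or CHESS-type event report or the registry record where held. Include the field in the data specification sent to registries that deliver only aggregated data.
4. Under objective 5, tabulate TE events as provoked, unprovoked or unknown.

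The cost is wording in three places and one field per event. The main downside is completeness. WBDR holds about 56% of the moderate patients and lists no such field, and the protocol does not show that every EUHASS-linked registry keeps the field in its extract. A substantial share of events may therefore be 'unknown'. The 56% is a share of all moderate patients; the share among eligible emicizumab users could differ.
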